3.0 Objectives

The design of this randomized clinical trial, which will be registered on clinicaltrials.gov, is a two-arm, 24-week, parallel-groups comparison of patient/provider dyads that will be randomly assigned to receive the results of the PGx test at the time the planned treatment is initiated (intervention group) or to have the results returned after 24 weeks of treatment as usual (delayed results group). The study will be conducted in up to 25 participating VA Medical Centers. In the intervention group, patient/provider dyads will be encouraged but not obligated to follow the recommendations resulting from the PGx battery to inform shared decision making. The primary aims and secondary aims of the trial are to *evaluate the utility of PGx testing in the treatment of MDD* and to understand how providers and patients use the information for shared treatment decision making, respectively. The study will test the following hypotheses:

1. Veterans with MDD whose care is guided by the results of the PGx battery (the intervention group) will have a higher rate of remission of depression than the delayed results group. (Primary Hypothesis)

2. Provider/patient dyads in the intervention group will use fewer medications that have potential gene-drug interactions based on commercial PGx test results than dyads in the delayed results group. (Primary Hypothesis)

3. Veterans in the intervention group will have better secondary outcomes than the delayed results group, including depressive symptom severity, side effect rate, treatment adherence rate, number of outpatient visits, and functional improvement. (Secondary Hypothesis)

4. Three months after receiving the PGx battery results, the delayed results group will show time-dependent changes in antidepressant prescribing and reductions in depressive symptoms that are similar in direction and magnitude to those seen in the intervention group. (Secondary Hypothesis)

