5.6.i. Adequacy of sample size. The single primary outcome is a set of repeated binary indicators of remission from depression. As we have a single outcome, we use a Type 1 error rate of 5%. Although we expect the intervention arm to be no less efficacious than the delayed results arm, we use a two-sided test. We also assume a 20% loss to dropout, distributed evenly over time, and across the two groups. The parameters that determine power are the base rate, which is the rate of treatment success expected in the delayed results arm, and the treatment effect. The anticipated remission rate in usual care is based on results from STAR*D [19]. For the base rate, we consider rates of 20-25-30-35%, and for the treatment effect, we look at effects of 5-6-7%. The study design has patients nested within providers, so it is possible that there will be small correlations between the results for two patients of the same provider. Accounting for nesting within provider should also address the nesting within sites [61]. Our design will have approximately 200 providers, with an average of ten patients per provider. The design effect due to provider is then 1+9*r, where r is our assumed provider intra-class correlation. Our sample of size 2000 is then equivalent to an "independent patients" sample of 2000/(1+9*r). We anticipate a low ICC, on the order of r<0.05. If we assume that r=0.05, then the design effect is 1.45, and the effective sample is 1379. For a base rate of 30%, and an assumed within-patient correlation of 0.4 or lower in a compound symmetry structure, then we have 82% power for a 5% treatment effect and 92% for the same effect in an ar(1) structure, with higher power for the same 5% effect with lower base rates. For r=0.01, where we have an effective sample size of 1835, we have power in excess of 90% for 5% effects, under either covariance structure. Even with a conservative estimate of r=0.1, the design effect is 1.9, yielding more than 80% power for treatment effects of 6% or greater.

5.6.j. Data management staffing. [name] and his staff will be responsible to coordinate the various data collection methods used in the clinical trial, and will provide support to the investigators, including site principal investigators to support additional exploratory hypotheses. In this section, we describe the methods that we will use to collect, store, and distribute data from the trial.

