- 4) In the delayed results group, there will be a decrease in the probabilities of antidepressants characterized as red or yellow prescribed in the 30 days after the release of the PGx test results, compared to the 30 days prior to release of results.

Rationale for amendments made– To clarify the intent of Hypothesis #4, it was agreed that this analysis would not be included in the primary paper.

Sample Size and Power Considerations.

We have two primary hypotheses, so we will test each at a 2.5% significance level, using two-sided tests.

The primary outcome for Hypothesis #1 is a set of repeated binary indicators of remission from depression. We assume a 20% loss to followup, distributed evenly over time, and across the two groups. The anticipated remission rate in usual care is based on results from STAR*D [2]. For the base rate, we consider rates of 20-25-30-35%, and for the treatment effect, we look at effects of about 5%. To account for correlations between the results for two patients of the same provider, we assume an intra-class correlation (ICC) of 0.05 or lower for providers, which should also address the nesting within sites [21]. We assume our design will have approximately 200 providers, with an average of ten patients per provider, so the design effect for an ICC of 0.05 is 1.45. For a base rate of 30% (based on results from STAR*D [2]), and an assumed within-patient correlation of 0.4 or lower in a compound symmetry structure, we have 82% power for a 5% treatment effect and 92% power for the same effect in an autoregressive (ar(1)) structure, with higher power for the same 5% effect with lower base rates. For a provider ICC of 0.01, where we have an effective sample size of 1835, we have power in excess of 90% for 5% effects, under either covariance structure.

For Hypothesis #2, the primary outcome is an ordinal response indicating the gene-drug interaction potential (coded as green, yellow, and red based on the PGx test for non, moderate and significant drug- gene interactions) of the initial prescription made during the intervention period. Assuming that the overall proportions in the sample are approximately 40%/40%/20% for green/yellow/red, respectively, then our sample of 2000 provides 80% power to detect a common odds ratio of 1.29 under a proportional odds model, at a significance level of 2.5%.

Data Analysis Plan for the Completed Sample.

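### The SAP tests Hypothesis #1 at two-sided 2.5% but reprints the power that the protocol gives at 5%, and the two documents set different significance levels for that hypothesis

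*SAP*

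**What the plan says.** Protocol 5.6.i (Adequacy of sample size) treats remission as the only primary outcome: "As we have a single outcome, we use a Type 1 error rate of 5"%, two-sided. For a 30% base rate, a within-patient correlation of at most 0.4 and provider ICC 0.05 (design effect 1.45, effective sample 1379) it reports: "then we have 82% power for a 5% treatment effect and 92% for the same effect in an ar(1) structure". At ICC 0.01 (effective sample 1835) it claims more than 90% under both structures. At ICC 0.1 it claims a design effect of 1.9, "yielding more than 80% power for treatment effects of 6% or greater". The protocol's Abstract and Section 3.0, however, each label two hypotheses as primary.

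The SAP (Sample Size and Power Considerations) splits the error rate: "We have two primary hypotheses, so we will test each at a 2.5% significance level, using two-sided tests". With the same base rate, effect, correlation, ICC, provider numbers and 20% loss, it reports "we have 82% power for a 5% treatment effect and 92% power for the same effect in an autoregressive (ar(1)) structure" and, at ICC 0.01, "we have power in excess of 90% for 5% effects, under either covariance structure". For Hypothesis #2 it reports 80% power to "detect a common odds ratio of 1.29 under a proportional odds model, at a significance level of 2.5"%.

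The SAP was finalised on 8/16/21. Protocol version 18 is dated October 22, 2021 and still carries the 5% text. Neither document says which one prevails.

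**The concern.** Halving the significance level with every other input fixed must lower power. Identical figures at 5% and at 2.5% therefore mean that at least one set is wrong as printed.

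Two things are at stake. First, the documents disagree on the level for the main clinical hypothesis, so a p-value between 0.025 and 0.05 would be read as positive under one and negative under the other. Second, the power quoted in the SAP does not belong to the test the SAP will run. The protocol's Significance section says that a failure to validate earlier findings would be a reason to modify or limit testing, so a null result should be set against the right figure.

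**Working it through.** **Inputs, common to both documents unless noted.** N = 2000 in two arms (1:1 assumed; no ratio is stated). Remission 30% against 35%. Five visits. Within-patient correlation 0.4. Design effect 1 + 9 × ICC, giving effective N of 1379 at ICC 0.05 and 1835 at ICC 0.01. Loss of 20%, spread evenly. Two-sided critical values are 1.960 (5%) and 2.241 (2.5%). CS is compound symmetry.

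**Reproducing the printed figures.** The power method is not named. Comparing mean remission over five visits, the variance factor is (1 + 4 × 0.4)/5 = 0.52 for CS and 0.379 for AR(1) with equally spaced visits. With 25% against 30% and no deduction for dropout, CS at ICC 0.05 gives z = 0.05/√[(0.1875 + 0.21)/(689.7/0.52)] = 2.89. Power is Φ(2.89 − 1.960) = 82.3% at 5% and Φ(2.89 − 2.241) = 74.1% at 2.5%. AR(1) gives 92.3% and 87.3%. At ICC 0.01 the values are 91.5% and 86.2% (CS), and 97.4% and 95.2% (AR(1)). So the printed figures match 5%, but only with rates and dropout handling that differ from the stated ones. Two other routes avoid relying on that match.

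**Method A: take 82% and 92% as correct at 5% and change only the level.** z = Φ⁻¹(power) + 1.960.
- CS, ICC 0.05: z = 0.915 + 1.960 = 2.875; Φ(2.875 − 2.241) = 73.7%.
- AR(1), ICC 0.05: z = 1.405 + 1.960 = 3.365; Φ(3.365 − 2.241) = 86.9%.
- ICC 0.01: multiply z by √(1.45/1.09). CS z = 3.316, power 91.3% falling to 85.9%. AR(1) z = 3.881, power 97.3% falling to 94.9%.

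**Method B: direct calculation from the stated inputs.** z = 0.05/√{(0.21 + 0.2275)/[(n_eff/2) × I]}, with I = 1′R⁻¹1. Without dropout I = 1.923 (CS) and 2.714 (AR(1)). With 4% lost before each of the five visits, I = 1.775 and 2.434.

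| Case | z (20% loss to none) | Power at 5% | Power at 2.5% | Printed |
|---|---|---|---|---|
| ICC 0.05, CS | 2.645–2.753 | 75–79% | 66–70% | 82% |
| ICC 0.05, AR(1) | 3.097–3.271 | 87–90% | 80–85% | 92% |
| ICC 0.01, CS | 3.050–3.175 | 86–89% | 79–82% | above 90% |
| ICC 0.01, AR(1) | 3.572–3.772 | 95–97% | 91–94% | above 90% |

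By Method B, CS at ICC 0.01 is already below 90% at 5%, so only part of that shortfall comes from the change of level. In the three cases that fall short at 2.5%, the level alone costs about 5 to 10 points by either method.

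**Which level does the SAP's Hypothesis #2 figure use?** With 40/40/20 proportions, 1 − (0.4³ + 0.4³ + 0.2³) = 0.864. The detectable odds ratio is exp√[12(z_α + 0.842)²/(2000 × 0.864)], which is 1.293 at 2.5% and 1.263 at 5%. The printed 1.29 is the 2.5% value.

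**The case against.** The mismatch itself is hard to dispute. The case against concerns how much it matters.

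- **The 5% statement sits in a sample-size section.** The protocol's analysis text for Hypothesis #1 (5.6.a) gives no level, and the SAP's level is stricter, so following the SAP cannot inflate type I error. This is fair. But nothing says the SAP governs, and the protocol carries the later date.
- **The practical loss of power may be nil.** Protocol 5.2 randomises within provider, so inflating the variance by 1.45 probably does not suit the treatment contrast. With no provider inflation, 2.5% and spread dropout, Method B gives about 83% (CS) and 93% (AR(1)), close to the printed values. This stands, and it is why no claim of underpowering is made. It does not rescue the printed figures, which are expressly tied to the 1.45 design effect.
- **The size of the error depends on an unnamed method.** This also stands. Both texts allow a correlation below 0.4, and by Method B 82% and 92% hold at 2.5% if it is about 0.2–0.25. Neither document states such a value, and the protocol's 5% figures would then be too low.
- **AR(1) spacing.** The Method B figures treat visits as equally spaced. If 0.4 is the correlation per four weeks and the actual visit weeks are used, AR(1) at ICC 0.05 and 2.5% is 85–89%, still under 92%.
- **Drafting history.** That the Hypothesis #1 paragraph was carried over without updating is an inference from the arithmetic; neither document says so.

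**Conclusion.** The point holds. The two documents give different levels for Hypothesis #1, and the SAP's power figures for it are not right at 2.5% under its own stated inputs. If the printed 82% and 92% are correct at 5%, the SAP overstates power at ICC 0.05 by about 8 points (CS) and 5 points (AR(1)), and its claim for ICC 0.01 fails under CS only. Direct calculation gives larger shortfalls at ICC 0.05. These sizes assume 1:1 allocation, a correlation of 0.4 and the documents' own design effect. The 2.5% split is itself a valid way to control error across two primary hypotheses. The unreconciled level is the more serious part, because it can decide how the main result is read.

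**What to change.** - **Protocol 5.6.i:** replace the single-outcome, 5% statement with the SAP's allocation of 2.5% to each of the two primary hypotheses.
- **SAP, Sample Size and Power Considerations:** recompute every Hypothesis #1 power figure at two-sided 2.5% with one named method, giving explicitly the two remission rates, the handling of the 20% loss, the visit spacing assumed for AR(1), and a treatment of provider clustering that reflects within-provider randomisation. Replace the three printed figures. Alternatively, label them as 5% values and print the 2.5% values beside them.
- **Protocol 5.6.i, ICC 0.1:** once the protocol adopts 2.5%, recompute the claim of more than 80% power for a 6-point effect as well. Under CS it goes from 85.2% to 77.7% by Method A (z = 3.004 for 30% against 36%), and is 70–74% at 2.5% by Method B.

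The cost is one recomputed SAP paragraph and a matching protocol edit. On the documents' own design effect the stated power becomes less favourable. Sample size, model and estimates are unaffected.

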PRIME Care (PRecision medicine In MEntal health Care) Funding Agency: VA Office of Research and Development Principal Investigator: [name] Version Number 18

October 22, 2021

Abstract

Background: In the last several years, commercial pharmacogenetic (PGx) testing for the selection of psychotropic medications has become widespread as a means of implementing "precision medicine", with some insurers electing to cover the cost of testing. These developments have put increasing pressure on the Veterans Health Administration to implement a mental health focused PGxs program, especially for treating depression, but without sufficient scientific study to support the utility of its clinical application.

Objectives: This project is designed to evaluate the utility of PGx testing in treating Major Depressive Disorder.

Methods: The project is a multi-site randomized clinical trial in which 2000 patient/provider dyads will be randomly assigned to receive the results of the PGx battery right after randomization (i.e., the intervention group) or after 6 months of treatment as usual (i.e., the delayed results group). The study will test the following primary hypotheses:

1. Veterans with major depressive disorder (MDD) whose care is guided by the results of the PGx battery (the intervention group) will have a higher rate of remission of depression than those in the delayed results group.

2. Provider/patient dyads in the intervention group will use fewer medications that have potential gene-drug based on commercial PGx tests results than dyads in than the delayed results group.

The patient inclusion and exclusion criteria are designed to target a population of patients with a major depression diagnosis who are starting or switching antidepressants.

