PRIME Care (PRecision medicine In MEntal health Care)
Statistical Analysis Plan

Derived 7/2020 with the publication of the Methods paper ([name] et al 2021)
Reviewed and finalized prior to Analysis by Executive Committee on 8/16/21

The following statistical analysis plan was specified in the methods paper submitted in July 2020 for publication [34]). The methods paper was an expansion of the original grant application, which had limited specificity in the approach to analysis. In the paper, the original hypotheses were unaltered from the grant application, although edited for clarity. Prior to the conclusion of the study and prior to initiation of analyses, the Statistical Analytic Plan was reviewed by the Executive Committee and approved as amended below. We highlight only substantive changes from the methods paper as noted.

The primary hypotheses to be tested in the clinical trial component are that:

- 1) During the first six months of treatment, Veterans with MDD whose care is guided by the results of the PGx battery (the intervention group) will have a higher rate of remission of depression than the delayed results group. Remission is defined as a Patient Health Questionnaire (PHQ-9) score of 5 or less.
- 2) Over the first 30 days after randomization, provider/patient dyads in the intervention group will use fewer antidepressant medications that have potential gene-drug interactions based on commercial PGx test results than dyads in the delayed results group.

Rationale for amendments made– Neither the grant nor the methods paper specified the time frame of Hypothesis #2. This was discussed and approved by the Executive Committee on 8/16/21, and 30 days was agreed upon to evaluate the time most proximal to receiving the PGx results. A secondary outcome will evaluate the proportion of days on which patients were prescribed antidepressants with a significant drug-gene interaction over the 24 weeks with the expectation of small changes in prescribing over time.

The secondary hypotheses are that:

- 3) Veterans in the intervention group will have better secondary outcomes than the delayed results group over the 24 weeks post-randomization, including rates of depression symptom response (as indicated by a 50% reduction in PHQ-9 score from baseline) and changes in PHQ-9 score.
 - Other secondary outcomes will include side effect rates, treatment adherence rate, and functional improvement.

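### Efficiency gain, not an error: Holm's step-down test in place of the fixed 2.5% split adds about 3 to 7 points of Hypothesis #1 power at Hypothesis #2's stated 80% power, at the same 5% family-wise error

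*SAP*

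**What the plan says.** The SAP, under Sample Size and Power Considerations, names two primary hypotheses, "so we will test each at a 2.5% significance level, using two-sided tests". It describes no step-down or other reallocation of alpha. The 5% family-wise level is not printed, but it is implied by two tests at 2.5% each.

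For Hypothesis #1 (remission) the SAP then states "we have 82% power for a 5% treatment effect and 92% power for the same effect", the first figure for compound symmetry and the second for AR(1), without attaching a significance level to either. For Hypothesis #2 (prescribing) it does attach one: the sample of 2000 "provides 80% power to detect a common odds ratio of 1.29 under a proportional odds model, at a significance level of 2.5" per cent.

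Protocol section 5.6.i says "As we have a single outcome, we use a Type 1 error rate of 5" per cent, and from that derives the same pair: "then we have 82% power for a 5% treatment effect and 92% for the same effect". Yet protocol section 3.0 labels Hypothesis #2 as primary too, ending it with "than dyads in the delayed results group. (Primary Hypothesis". The SAP header reads "Reviewed and finalized prior to Analysis by Executive Committee on 8/16/21". The protocol version is dated "October 22, 2021", so the single-outcome, 5% text is still in the later document.

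**The concern.** The fixed split judges each hypothesis at 2.5% whatever the other shows. Holm tests the smaller p-value at 2.5% and, if that is rejected, the other at 5%. It holds family-wise error at 5% under any dependence between the tests, and it never loses a rejection that the split would have made.

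The difference shows in one situation. If Hypothesis #2 is rejected at 2.5% and Hypothesis #1 has p between 0.025 and 0.05, the SAP must call the remission result negative, although 5% family-wise control would allow a positive claim. If Hypothesis #2 is not rejected at 2.5%, nothing changes for Hypothesis #1.

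There is also a documentation problem that does not depend on Holm. The same two powers cannot be correct at both 5% and 2.5% when base rate, effect, provider ICC and within-patient correlation are the same. If they belong to 5%, the SAP overstates its Hypothesis #1 power.

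**Working it through.** **Inputs.** Hypothesis #1 power 82% / 92% (SAP; protocol 5.6.i). Hypothesis #2 power 80% at 2.5% (SAP). Two-sided critical values: 1.960 at 5% and 2.241 at 2.5%. Pairs below are compound symmetry / AR(1). Independent test statistics are assumed unless a correlation is given; the documents do not address this.

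**Can the printed Hypothesis #1 powers be reproduced?** I used a two-proportion test on the time-averaged remission rate, with n per arm = (2000 / 1.45 / 2) / v. For five visits at correlation 0.4, v = (1 + 4 × 0.4) / 5 = 0.52 under compound symmetry and 0.379 under AR(1).

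| Rates | Two-sided level | Dropout | Power |
|---|---|---|---|
| 30% v 35% | 2.5% | none | 69.4% / 83.7% |
| 30% v 35% | 2.5% | 20%, even | 65.6% / 80.3% |
| 30% v 35% | 5% | none | 78.5% / 89.7% |
| 30% v 35% | 5% | 20%, even | 75.2% / 87.2% |
| 25% v 30% | 5% | none | 82.3% / 92.2% |
| 25% v 30% | 2.5% | none | 74.0% / 87.3% |

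The SAP's stated inputs at 2.5% do not give 82% / 92%. A close match comes at 5%, with rates of 25% and 30% and no dropout. This suggests, but does not prove, that the figures were carried over from the 5% design. Both readings are therefore worked through.

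**Hypothesis #2.** For a proportional odds model with proportions 0.4, 0.4, 0.2: √[2000 × (1 − 0.064 − 0.064 − 0.008) / 12] × ln 1.29 = 12.0 × 0.2546 = 3.056. Power = Φ(3.056 − 2.241) = 79.2%, which agrees with the stated 80%.

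**Holm gain for Hypothesis #1.** Under independence:

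gain = [power at 5% − power at 2.5%] × P(Hypothesis #2 rejected at 2.5%)

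*Reading A: 82% / 92% are 5%-level powers.*
- Standardised effect θ = 1.960 + z(0.82) = 2.875, and 1.960 + z(0.92) = 3.365.
- Power at the fixed 2.5% = Φ(θ − 2.241) = 73.7% / 86.9%.
- Largest possible gain = 8.3 / 5.1 points.
- At 80% Hypothesis #2 power, the gain is 6.6 / 4.1 points, so Holm gives 80.3% / 91.0%.

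*Reading B: 82% / 92% are 2.5%-level powers.*
- θ = 2.241 + z(0.82) = 3.157, and 2.241 + z(0.92) = 3.646.
- Power at 5% = 88.4% / 95.4%.
- Largest possible gain = 6.4 / 3.4 points.
- At 80% Hypothesis #2 power, the gain is 5.1 / 2.7 points, so Holm gives 87.1% / 94.7%.

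**Sensitivity of the gain (points).**

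| Case | Reading A | Reading B |
|---|---|---|
| Hypothesis #2 power 80% | 6.6 / 4.1 | 5.1 / 2.7 |
| As above, test correlation −0.3 to 0.5 | 5.8–7.2 / 3.0–4.6 | 4.1–5.7 / 1.8–3.1 |
| Hypothesis #2 power about 62% (1.45 design effect applied to it, an assumption) | 5.1 / 3.1 | 4.0 / 2.1 |
| Hypothesis #2 power 50% | 4.2 / 2.5 | 3.2 / 1.7 |
| No Hypothesis #2 effect (rejected 2.5% of the time) | 0.2 / 0.1 | 0.2 / 0.1 |
| Provider ICC 0.01, Hypothesis #1 power 91.4% / 97.4% (25% v 30% variant), Hypothesis #2 power 80% | 4.2 / 1.8 | 2.9 / 1.0 |

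**Other quantities.** For the fixed split to match Holm's power under Reading A, the sample would have to grow by ((2.241 + z(0.8034)) / 2.875)² = 1.159, or ((2.241 + z(0.9099)) / 3.365)² = 1.133. That is about 2,318 or 2,266 patients instead of 2,000. Hypothesis #2 gains as well: θ = 2.241 + 0.842 = 3.083, and its power at 5% is 86.9%. Holm therefore lifts it from 80% to between 0.80 + 0.069 × 0.737 = 85.1% and 0.80 + 0.069 × 0.92 = 86.4%. With both nulls true and independent, family-wise error is 1 − 0.975² = 4.94%.

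**The case against.** The fixed split is a legitimate prespecified choice, and nothing in the documents contradicts it. It has real merits. Its 97.5% intervals agree with its tests, which matters because protocol section 5.6.a promises confidence intervals and p-values. It also keeps the remission verdict separate from the prescribing verdict, whereas under Holm a remission p of 0.03 counts or not according to what happened to prescribing. These points stand; they are why this is an improvement and not a correction.

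The size of the gain is also open to challenge. The 80% Hypothesis #2 power is the power at a detectable odds ratio of 1.29, not a forecast, and the check reproduces it without any allowance for provider clustering. The SAP assumes a provider ICC of 0.05 or lower, and at 0.01 the gain is only about 1 to 4 points. That narrows the benefit, but in no scenario is a rejection lost. The sample-size equivalent only illustrates the scale, since the planned sample is 2,000.

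Timing is the most serious point. Relaxing a rejection threshold after the Executive Committee finalised the SAP invites questions, and the documents do not show whether results by arm have been seen. If they have, the split should stay. The power discrepancy is a separate matter and needs fixing either way.

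**Conclusion.** The point holds as an efficiency improvement to a valid plan. At Hypothesis #2's stated 80% power, with independent tests and the printed 82% / 92%, Holm adds 6.6 / 4.1 points to Hypothesis #1 power if those figures are at 5%, or 5.1 / 2.7 points if they are at 2.5%. The first reading is the more likely, given the identical protocol text and the close match at 5%. On that reading, the SAP's actual Hypothesis #1 power under the fixed split is 73.7% / 86.9%, not 82% / 92%. The gain scales with the chance that Hypothesis #2 is rejected, from almost nothing if it has no effect to at most 8.3 / 5.1 points. The conflict between one outcome at 5% and two hypotheses at 2.5% is a documentation fault whatever is decided about Holm.

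**What to change.** 1. If no unblinded comparison has been made, replace the testing sentence by a dated, justified SAP amendment along these lines: the two primary hypotheses are tested two-sided with Holm's step-down procedure at family-wise 5%, the smaller p-value at 2.5% and, if it is rejected, the other at 5%. If results by arm have been seen, keep the 2.5% split.
2. Reconcile protocol section 5.6.i with the two primary hypotheses in section 3.0 and the SAP.
3. Restate Hypothesis #1 power at the level actually used, and name that level beside the figure.
4. With Holm, report 97.5% and 95% intervals side by side and state that the Holm decision governs the claim.

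The cost is one SAP sentence with its rationale, one protocol edit and one recalculated power statement; no new data are needed. The drawback is that intervals match the tests less directly. With Hypothesis #2 not rejected and Hypothesis #1 at p = 0.03, the 95% interval excludes no effect although Holm does not reject. Item 4 is there to handle this.
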